#### 11.42 Non-Target Lesions & Non-Target Lymph Nodes

Non-measurable sites of disease (Section 11.22) are classified as non- target lesions or non-target lymph nodes and should also be recorded at baseline. These lesions and lymph nodes should be part of the response assessment as detailed in Section 11.433 or 11.442.

**11.43 RESPONSE CRITERIA FOR PATIENTS WITH MEASUREABLE TARGET LESIONS/LYMPH NODES**

11.431 All target lesions and target lymph nodes followed by CT or MRI must be measured on re-evaluation at evaluation time points specified in Section 11.1. Specifically, a change in objective status to either a PR or CR cannot be done without re-measuring target lesions and target lymph nodes.

**Note:** Non-target lesions and non-target lymph nodes should be evaluated at each assessment, especially in the case of first response or confirmation of response. In selected circumstances, certain non-target organs may be evaluated less frequently. For example, bone scans may need to be repeated only when complete response is identified in target disease or when progression in bone is suspected.

**11.432 Evaluation of Target Lesions**

- Complete Response (CR): All of the following must be true:
  - a. Disappearance of all target lesions.
  - b. Each target lymph node must have reduction in short axis to <1.0 cm (if short axis being used for measurement) or have reduction in long axis to < 0.7 cm (if long axis is being used for measurement).
  - c. For patients without detectable thyroglobulin antibodies, serum thyroglobulin on suppression must be measured to be <0.2 ng/ml. If a center does not have a thyroglobulin assay that reads to <2 ng/ml, then a TSH-stimulated Tg <1 ng/ml would be required to confirm complete response. For patients with detectable thyroglobulin antibodies, assessment of thyroglobulin will not be necessary for assessment of complete response.
- Partial Response (PR): At least a 30% decrease in PBSD (sum of the longest diameter for all target lesions plus the sum of the long or short axis of all the target lymph nodes (depending on which axis is being used for assessments) at current evaluation) taking as reference the BSD (see Section 11.41).
- Progression (PD): At least one of the following must be true:
  - a. At least one new malignant lesion, which also includes any lymph node that was normal at baseline (<1.0 cm short axis) and increased to  $\geq 1.0$  cm short axis and is deemed to be malignant during follow-up.
  - b. At least a 20% increase in PBSD (sum of the longest diameter for all target lesions plus the sum of the long or short axis of all the target lymph nodes (depending on which axis is being used for assessments) at current evaluation) taking as reference the MSD (Section 11.41). In addition, the PBSD must also demonstrate an absolute increase of at least 0.5 cm from the MSD.

- c. See Section 11.32 for details in regards to the requirements for PD via FDG-PET imaging.
- Stable Disease (SD): Neither sufficient shrinkage to qualify for PR, nor sufficient increase to qualify for PD taking as reference the MSD.

#### 11.433 Evaluation of Non-Target Lesions & Non-target Lymph Nodes

- Complete Response (CR): All of the following must be true:
  - a. Disappearance of all non-target lesions.
  - b. Each non-target lymph node must have a reduction in short axis to <1.0 cm.
  - c. For patients without detectable thyroglobulin antibodies, stimulated serum thyroglobulin must be measured to be undetectable. For patients with detectable thyroglobulin antibodies, assessment of thyroglobulin will not be necessary for assessment of complete response.
- Non-CR/Non-PD: Persistence of one or more non-target lesions or non-target lymph nodes.
- Progression (PD): At least one of the following must be true:
  - a. At least one new malignant lesion, which also includes any lymph node that was normal at baseline (<1.0 cm short axis) and increased to  $\geq 1.0$  cm short axis and is deemed to be malignant during follow-up.
  - b. Unequivocal progression of existing non-target lesions and non-target lymph nodes. (NOTE: Unequivocal progression should not normally trump target lesion and target lymph node status. It must be representative of overall disease status change.)
  - c. See Section 11.32 for details in regards to the requirements for PD via FDG-PET imaging.

#### 11.434 Overall Objective Status for Patients with Measureable Target Lesions/Lymph Nodes

The overall objective status for an evaluation is determined by combining the patient's status on target lesions, target lymph nodes, non-target lesions, non-target lymph nodes, and new disease as defined in the following tables. Serum thyroglobulin measurements will not be used in determining overall response, except for designating a complete response (as detailed in Section 11.432 and in the table below):

Target Lesions & Target Lymph Nodes	Non-Target Lesions & Non-Target Lymph Nodes	New Sites of Disease	Overall Objective Status
CR	CR	No	CR*
CR	Non-CR/Non-PD	No	PR
PR	CR Non-CR/Non-PD	No	PR
CR/PR	Not All Evaluated**	No	PR***
SD	CR Non-CR/Non-PD Not All Evaluated**	No	SD
Not all Evaluated	CR Non-CR/Non-PD* Not All Evaluated**	No	Not Evaluated (NE)
PD	Unequivocal PD CR Non-CR/Non-PD Not All Evaluated**	Yes or No	PD
CR/PR/SD/PD/Not all Evaluated	Unequivocal PD	Yes or No	PD
CR/PR/SD/PD/Not all Evaluated	CR Non-CR/Non-PD Not All Evaluated**	Yes	PD

\* CR designation may also require serum thyroglobulin assessment as detailed in Section 11.432.

\*\* See Section 11.431

\*\*\* NOTE: This study uses the protocol RECIST v1.1 template dated 2/16/2011. For data collection and analysis purposes the objective status changed from SD to PR in the ACCRU protocol RECIST v1.1 template as of 2/16/2011 and to match RECIST v1.1 requirements.

#### 11.44 **RESPONSE CRITERIA FOR PATIENTS WITH NON-MEASUREABLE, NON-TARGET LESIONS/LYMPH NODES ONLY**

11.441 Lesions and lymph nodes should be followed by CT or MRI at time points specified in Section 11.1.

11.442 Structural Evaluation of Non-Target Lesions & Non-target Lymph Nodes

These guidelines inform how non-target lesions and non-target lymph nodes should be assessed for all patients enrolled on trial.

- Complete Response (CR): All of the following must be true:
  - a. Disappearance of all non-target lesions.
  - b. Each non-target lymph node must have a reduction in short axis to <1.0 cm.
  - c. For patients without detectable thyroglobulin antibodies, serum thyroglobulin on suppression must be measured to be < 0.2 ng/ml.

If a center does not have a thyroglobulin assay that reads to  $\leq 2$  ng/ml, then a TSH-stimulated TG  $<1$  ng/ml would be required to confirm complete response. For patients with detectable thyroglobulin antibodies, assessment of thyroglobulin will not be necessary for assessment of complete response.

- Non-CR/Non-PD: Persistence of one or more non-target lesions or non-target lymph nodes.
- Progression (PD): At least one of the following must be true:
  - a. At least one new malignant lesion, which also includes any lymph node that was normal at baseline ( $<1.0$  cm short axis) and increased to  $\geq 1.0$  cm short axis and is deemed to be malignant during follow-up.
  - b. Unequivocal progression of existing non-target lesions and non-target lymph nodes. (NOTE: Unequivocal progression should not normally trump target lesion and target lymph node status. It must be representative of overall disease status change.)
  - c. See Section 11.32 for details in regards to the requirements for PD via FDG-PET imaging.

11.443

#### **Overall Objective Status for Patients with Non-Measurable, Non-Target Lesions/Lymph nodes**

The overall objective status for an evaluation is determined by:

- Structural assessment of lesions/lymph nodes as detailed in Section 11.442.
- For the “non-CR/non-PD” structural category, measurement of the serum TG in the context of suppressed TSH (and negative TG antibody) will be used to determine the final response designation (the exception is for the assessment of complete response, which requires measurement of a stimulated TG, see chart below).

Non-Target Lesions & Non-Target Lymph Nodes	Serum Thyroglobulin (TG)* (or TG antibody)	New Sites of Disease	Overall Objective Status
CR	TG < 0.2 ng/ml on TSH suppression* OR stimulated TG < 0.1 ng/ml (see 11.442)	No	CR
CR	TG ≥ 0.2 ng/ml on TSH suppression* OR stimulated TG > 0.1 ng/ml (see 11.442)	No	Assess as per Non-CR/Non-PD
Non-CR/Non-PD	50% or more reduction compared to baseline Tg WITHOUT a 25% or more increase compared to the lowest TG measured on study (baseline or nadir)*	No	PR
Non-CR/Non-PD	25% or more increase compared to the lowest TG measured on study* (baseline or nadir)	No	PD
Non-CR/Non-PD	Less than 50% reduction compared to baseline TG WITHOUT a 25% or more increase compared to the lowest TG measured on study* (baseline or nadir)	No	SD
Non-CR/Non-PD	New detection of TG antibody	No	PD
Not All Evaluated	25% or more increase compared to lowest TG measured on study Tg* (baseline or nadir)	No	PD

Non-Target Lesions & Non-Target Lymph Nodes	Serum Thyroglobulin (TG)* (or TG antibody)	New Sites of Disease	Overall Objective Status
Not All Evaluated	WITHOUT 25% or more increase compared to lowest TG measured on study Tg* (baseline or nadir)	No	NE
Uequivocal PD	Any serum TG result or TG antibody result, including failure to complete the measurement as per protocol	Yes or No	PD
CR Non-CR/Non-PD Not All Evaluated	Any serum TG or TG antibody result, including failure to complete the measurement as per protocol	Yes	PD
CR Non-CR/Non-PD Not All Evaluated	TG was not evaluated or not evaluated in the context of TSH suppression*	No	NE

\* TG will be measured in the context of a suppressed TSH ( $\leq 0.4$  mcU/ml) and negative TG antibody, except for the designation of CR which may require TG measurement in the context of TSH stimulation (see 11.442). For the primary endpoint, the serum TG value designated for the 6-month assessment (6 months after therapeutic  $^{131}\text{I}$  is administered) will be used. If the 6-month serum TG is initially measured in the context of a TSH  $>0.4$  mcU/ml, then every effort should be made to repeat this assessment until a serum TG value is obtained in the context of a TSH  $\leq 0.4$  mcU/ml, even if it requires obtaining the measurement outside of the protocol-defined  $\pm 1$  week window. Serum TG values that have to be obtained outside this protocol-defined window to ensure it is measured in the context of TSH  $\leq 0.4$  mcU/ml will still be used for the primary assessment of response.

11.45 **NOTE:** On this study, patients with clinical, radiographic, or biochemical (i.e., thyroglobulin, if applicable) evidence of progression of disease (as described above) on assessments prior to the 6-month disease evaluation (i.e. the scans and evaluations performed 6 months after therapeutic  $^{131}\text{I}$  is administered) will be allowed to continue on study treatment and/or evaluations given the potentially delayed therapeutic benefit of  $^{131}\text{I}$ , effects of Thyrogen™, etc. For patients with clinical, radiographic or biochemical evidence of progression of disease on assessments prior to the 6 month disease evaluation, the final objective response assessment at 6 months will be based

upon a comparison between the 6 month radiologic scan(s)/evaluations and the baseline, pre-treatment radiologic scans (and serum thyroglobulin measurements if applicable).

11.46 Symptomatic Deterioration: Patients with global deterioration of health status requiring discontinuation of treatment without objective evidence of disease progression at that time, and not either related to study treatment or other medical conditions, should be reported as PD due to “symptomatic deterioration.” Every effort should be made to document the objective progression even after discontinuation of treatment due to symptomatic deterioration. A patient is classified as having PD due to “symptomatic deterioration” if any of the following occur that are not either related to study treatment or other medical conditions:

- Weight loss >10% of body weight.
- Worsening of tumor-related symptoms.
- Decline in performance status of >1 level on ECOG scale.

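### The thyroglobulin rules for complete response disagree across Sections 11.432, 11.433, 11.442 and 11.443, and two rows of the 11.443 table overlap

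*Combined protocol and SAP*

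**What the plan says.** Four places in protocol Section 11 set the TG condition for CR in patients without TG antibodies.

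- Section 11.432 (target lesions) asks for a suppressed TG below 0.2 ng/ml, then adds a fallback: "If a center does not have a thyroglobulin assay that reads to <2 ng/ml, then a TSH-stimulated Tg <1 ng/ml would be required".
- Section 11.433 (non-target lesions in patients with measurable disease) has a different rule: "stimulated serum thyroglobulin must be measured to be undetectable".
- Section 11.442 (patients with non-measurable disease only, although its opening line extends it to everyone enrolled) says "serum thyroglobulin on suppression must be measured to be < 0.2 ng/ml". It repeats the fallback, starting "If a center does not have a thyroglobulin assay that reads to", with a trigger of 2 ng/ml or lower and the same stimulated limit of below 1 ng/ml.
- Section 11.443 says in its text that CR needs a stimulated TG. Row 1 of its table nevertheless gives CR for a suppressed TG below 0.2 or "stimulated TG < 0.1 ng/ml (see 11.442". Row 2 covers a suppressed TG of 0.2 or more, or "stimulated TG > 0.1 ng/ml (see 11.442", and its outcome is "Assess as per Non-CR/Non-PD". In that category a rise of 25% or more over the lowest on-study TG is progressive disease (PD). A fall of 50% or more from baseline without such a rise is partial response (PR).

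Section 3.16 allows any TG assay but requires the same one throughout, and sets a minimum baseline TG of 10 ng/ml for patients with non-measurable disease. Section 16.2 counts PR or CR at 6 months as a response.

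**The concern.** These limits feed the primary endpoint and, through the same Section 11 criteria, progression-free survival (PFS). If two sections give different results for one patient, whoever scores that patient has to choose between them without a written rule.

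There are three separate defects. The stimulated limit takes three values, and the sections disagree on whether a stimulated TG is needed at all. The fallback cannot be satisfied by the assays it is meant for. Rows 1 and 2 of the 11.443 table are not mutually exclusive. The third defect is the one that can turn a responder into a non-responder.

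**Working it through.** **The rules side by side**

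| Section | Suppressed TG for CR | Stimulated TG for CR | When the stimulated value applies |
|---|---|---|---|
| 11.432 | <0.2 | <1 | assay does not read to <2 |
| 11.433 | none stated | undetectable | always |
| 11.442 | <0.2 | <1 | assay does not read to ≤2 |
| 11.443 text | none stated | required, no value | always |
| 11.443 table, row 1 | <0.2 | <0.1 | as an alternative (OR) |

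The suppressed limit agrees wherever it appears. The stimulated limit differs tenfold between 11.442 and the table that cites it.

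**The fallback, by assay limit**

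- Limit above 2 ng/ml (say 2.5): the fallback opens, but the assay cannot show a value below 1, and Section 3.16 rules out changing assay. CR cannot be confirmed.
- Limit above 0.2 and up to 2 ng/ml: the assay cannot show a value below 0.2, and the fallback does not open. There is no route to CR under 11.442.
- Limit of 0.2 ng/ml or lower: the suppressed rule works and the fallback is not needed.

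**The row overlap**

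Take a patient with non-measurable disease, negative antibody, all lesions gone, a sensitive assay and baseline TG 10. The suppressed nadir is 0.10, month-6 suppressed TG is 0.15 and stimulated TG is 0.5.

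1. Section 11.442: 0.15 < 0.2, so CR.
2. Table row 1: 0.15 < 0.2 satisfies one side of the OR, so CR.
3. Table row 2: 0.5 > 0.1 satisfies one side of its OR, so the patient is scored as Non-CR/Non-PD.
4. There, 0.15/0.10 − 1 = 50%, which is at least 25%, so PD. The fall from baseline is 1 − 0.15/10 = 98.5%.

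With a nadir of 0.15 and no rise, row 1 gives CR and row 2 gives PR. A stimulated TG of exactly 0.1 meets neither stimulated condition.

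**When responder status changes**

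With baseline TG of at least 10, a TG of 1 or less is a fall of at least 1 − 1/10 = 90%. Without a 25% rise over nadir, a patient sent to row 2 is therefore PR and still a responder. In measurable disease, Section 11.434 uses TG only to designate CR, so the dispute there is CR versus PR. The flip needs three things together: non-measurable disease only, a suppressed and a stimulated TG that point to different rows, and a rise of at least 25% over nadir. At a nadir of 0.10 that rise is 0.025 ng/ml.

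**Possible size**

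The plan's sample size reproduces. With z(0.85) = 1.036, z(0.80) = 0.842 and mean rate 0.525:

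n = [1.036·√(2·0.525·0.475) + 0.842·√(0.40·0.60 + 0.65·0.35)]² / 0.25² = 27.4, so 28 per arm. Power at 28 is 80.6%.

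The documents give no frequency for the flip, so the shares below are assumptions. Both response rates are multiplied by (1 − share).

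| Share of responders moved to PD, both arms | Power at 28 per arm |
|---|---|
| 0% | 80.6% |
| 2% | 79.5% |
| 5% | 77.7% |
| 10% | 74.8% |

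One responder lost in the selumetinib arm only (0.65 − 1/28 = 0.614) gives 71.9%.

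**The case against.** The strongest reply is that the value that matters for the primary endpoint is consistent. Suppressed TG below 0.2 appears in 11.432, 11.442 and 11.443. Footnote 18 of the Test Schedule requires the 6-month TG under suppression for patients with non-measurable disease, and the footnote to the 11.443 table says only that CR may call for a stimulated value. The Test Schedule lists Thyrogen at Week 4 and not afterwards, so few patients should have a month-6 stimulated TG. The trigger of 2 may be a slip for 0.2. In measurable disease, 11.434 refers to 11.432 for the TG condition, which largely settles the conflict with 11.433. Best overall response in Section 16.3 counts confirmed PR or CR, so CR versus PR does not matter there either. For PFS, Section 16.3 lets the physician disregard progression seen within 6 months of radioiodine.

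Most of this stands, and it limits the size of the problem. It does not remove it. The 11.443 text still says that CR needs a stimulated TG, the slip (if it is one) appears in two sections, and nothing says which row prevails. Section 11.45 does not help the patient above: its comparison with baseline covers progression found before the 6-month evaluation, not a first rise at month 6.

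A reader might go further and infer that the gap between <1 and <0.1 by itself moves patients from CR to PD, for example a patient on an assay with a limit of 0.5, suppressed TG 0.65 after a nadir of 0.5, and stimulated TG 0.8. The literal text does not support that. An assay reading to 0.5 does not open the fallback, and 0.65 fails the suppressed limit in both 11.442 and the table. That patient is CR under 11.442 only if the trigger is read as 0.2.

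**Conclusion.** The CR thyroglobulin rules are inconsistent as written and should be reconciled. There are three stimulated limits, a fallback that cannot be met, a range of assay limits with no route to CR, and two overlapping table rows.

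The effect on the primary endpoint is narrow. It is confined to patients with non-measurable disease only, expected to be 60% of accrual (0.60 × 56 ≈ 34 evaluable patients). Within that group it needs both a discordant stimulated TG and a rise of at least 25% over nadir. It is likely rare, though the documents give no frequency; the power figures rest on assumed shares and only show the scale. Elsewhere the conflict is CR versus PR and responder status holds.

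A reader might also infer that the 25% nadir rule is itself at fault, or that the suppressed limits conflict. Neither follows: the nadir rule is a stated endpoint choice, and the suppressed limits agree.

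**What to change.** Before unblinding, amend Sections 11.432, 11.433, 11.442 and 11.443 to carry one set of CR thyroglobulin rules:

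- keep the suppressed limit, which already agrees;
- state a single stimulated limit and repeat it wherever a stimulated TG is mentioned;
- make the assay trigger consistent with the suppressed limit, so that every permitted assay falls under a rule and the fallback can be met by the assays that open it;
- align the 11.443 text with its table on whether a stimulated TG is required or is an alternative;
- make rows 1 and 2 mutually exclusive by stating which TG decides when both are available, and assign the boundary value to one row.

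The cost is an amendment to wording and a blinded recheck of any structural CR already scored. If the stimulated value is made decisive, the Test Schedule must be reconciled with that, since it lists no stimulation after Week 4. The 25% nadir rule need not change. Exempting structural CR from it would be a new response and progression rule affecting the primary endpoint and PFS, and would need its own justification.

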## **12.0 Descriptive Factors**

12.1 Number of prior  $^{131}\text{I}$  treatments: 0 vs. 1 vs. 2 vs. 3 vs. 4 or more.

12.2 Previous chemotherapy/targeted therapy for thyroid cancer: Yes vs. No.

12.3 Prior RT: Yes vs. No.

12.4 Thyroid histology: (papillary, follicular, poorly differentiated, and other respective variants).

## **13.0 Treatment/Follow-up Decision at Evaluation of Patient**

13.1 Patients who are CR, PR, or SD will continue treatment/assessment per protocol. Patients that are non-PD after completing treatment will be followed during the observation phase as outlined in Section 4.0: 1 month post-treatment, 3 months post-treatment, followed by every 3 months until 12 months post-treatment when patients will be followed every 6 months for a maximum of 2 years (+/- 3 months) from randomization.

13.2 Patients who develop PD while receiving therapy or undergoing protocol assessment will be followed in the event monitoring phase (see section 18). However, it is possible that patients will have PD early in the study and still demonstrate benefit from the study treatment later in the study for several reasons: 1) selumetinib alone prior to RAI may not have significant clinical efficacy, 2) Thyrogen™ stimulation can transiently increase tumor size which can be mistaken for disease progression; 3) the therapeutic effects of RAI can be delayed; and 4) evidence of progression may be evident prior to administration of RAI. Hence, patients with evidence of radiographic, clinical or biochemical (i.e. thyroglobulin, if applicable) PD noted prior to the 6-month disease evaluation (i.e. the scans and evaluations performed 6 months after therapeutic  $^{131}\text{I}$  is administered) may remain on treatment/assessment at the discretion of the treating physician. If, in the opinion of the treating physician, these patients are unlikely to demonstrate benefit with subsequent clinical assessments, the patients will be classified as having PD and will be followed in the event monitoring phase (see Section 18.0).

13.3 Patients who go off protocol treatment for reasons other than PD will go to the event-monitoring phase per Section 18.0.

13.4 Patients who develop CNS PD at any time should go to event monitoring. These patients should receive treatment if deemed clinically indicated by the treating physician(s).

13.5a A patient is deemed ineligible if after registration, it is determined that at the time of registration, the patient did not satisfy each and every eligibility criteria for study entry. The patient may continue treatment off-protocol at the discretion of the physician as long as there are no safety concerns, and the patient was properly registered. The patient will go directly to the event-monitoring phase of the study (or off study, if applicable).

- If the patient received treatment, all data up until the point of confirmation of ineligibility must be submitted. Event monitoring will be required per Section 18.0 of the protocol.
- If the patient never received treatment, on-study material must be submitted. Event monitoring will be required per Section 18.0 of the protocol.

13.5b A patient is deemed a major violation, if protocol requirements regarding treatment in cycle 1 of the initial therapy are severely violated such that evaluation of the primary end point is significantly compromised. All data up until the point of confirmation of a major violation must be submitted. The patient will go directly to the event-monitoring phase of the study. The patient may continue treatment off-protocol at the discretion of the physician as long as there are no safety concerns, and the patient was properly registered. Event monitoring will be required per Section 18.0 of the protocol.

13.5c A patient is deemed a cancel if he/she is removed from the study for any reason before any study treatment is given. On-study material and the End of Active Treatment/Cancel Notification Form must be submitted. No further data submission is necessary.

